#### (6) Incidence of AE (adverse event)

Evaluation time: During the whole clinical trial process.

Formula: Incidence of adverse events = number of subjects with adverse events in this group/number of all subjects in this group  $\times$  100%.

**Definition:** An adverse event is any untoward medical occurrence in a clinical investigation, whether or not related to the device. It is necessary to analyze the postoperative vital signs and laboratory tests (blood routine, biochemical indicators, etc.).

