#### 8.2.5.5 Other examinations

(1) Intraoperative observation items: operation starting time, operation ending time (24 h clock h/min) , anastomosis starting time, anastomosis ending time (s), resected lobe or segment , intraoperative blood

 Mainly record drugs that affect healing (e.g., antineoplastic agents, corticosteroids) or coagulation.

 Body mass index (BMI) = weight (kg)  $\div$  height (m^2)

 For laboratory examinations, the reports/results issued by our hospital within 7 days prior to surgery can be accepted.

 For imaging examination, the reports/results issued by our hospital within 1 month prior to surgery can be accepted.

 In case of air leakage and bleeding at the staple line, the investigators may decide whether the subject will receive

relevant examinations according to actual needs.

 The duration from the time of thoracotomy to chest closure is recorded.

 Right upper lobe, right middle lobe, right lower lobe, left upper lobe and left lower lobe.

loss, whether the transection and anastomosis are successful, whether the cutting staple line is complete, whether there is leakage in the cutting staple line, whether there is bleeding in the cutting staple line, whether there is air leakage in the staple line, whether there is conversion to thoracotomy , number of stitches for staple line repair , whether there is staple line dehiscence , whether there are other complications , evaluation on the stapler operating performance;

- (2) Use of device : models and specifications of electric-endoscopic stapler, reload models and specifications, device defect;
- (3) Postoperative follow-up observation: whether there is anastomotic line bleeding , whether there are other complications , duration of chest tube drainage (days), whether there is anastomotic infection;
- (4) Routine observation items: adverse events/serious adverse events, concomitant and combined medication, protocol deviations.

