## 8.2.7.1 1st visit 1/before surgery (Day $-7 \sim 0$ )

- (1) The ICF form shall be signed;
- (2) Screening subjects according to the inclusion and exclusion criteria;
- (3) Randomized grouping;
- (4) Recording demographic data, current medical history and past medical history are recorded;
- (5) Examining vital signs;
- (6) Performing preoperative imaging examination (CT/MRI examination);
- (7) Performing laboratory examinations (blood routine, coagulation routine, blood biochemistry, heart examination, pulmonary function test, arterial blood gas analysis, blood pregnancy test);

 If yes, please specify the reason and whether it is related to the stapler. If the investigators use other devices for repair, it is necessary to record the product name and the quantity used, and finally replace the number of repair needles with the quantity used.

 Truthfully record the model and amount used in the clinical trial.

 If corresponding symptoms occur, the reasons for confirming the event should also be briefly described, so as to facilitate the review. The diagnosis is confirmed by thoracoscopy or second surgical exploration.

- (8) Recording concomitant and concomitant medications;
- (9) Recording protocol deviations;

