### 8.2.7.3 $3^{rd}$ visit 3/after surgery (Day 7 ± 2 days)

- (1) Examining vital signs;
- (2) Conducting laboratory examinations (blood routine, coagulation routine, blood biochemistry);
- (3) Conducting postoperative imaging examinations (angiography, thoracoscopy) ;
- (4) Postoperative follow-up observation;
- (5) Recording concomitant and combined medications;
- (6) Recording adverse events and serious adverse events;

Recording protocol deviations;

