# 9.7 Statistical Methods of Data, Together with Processing Methods of Missing, Unused or Wrong Data and Unreasonable Data

#### 9.7.1 Statistical method for data

Statistical analysis is performed using the SAS 9.1 software.

Statistical description on all data, including demographic data, baseline data, all efficacy indicators and all safety data shall be performed. Measurement data will be statistically described using mean, standard deviation, minimum, maximum, median, 25th percentile and 75th percentile; enumeration data will be statistically described using frequency and percentage.

The primary effectiveness evaluation indicator (device cutting and anastomosis success rate) is evaluated by the confidence interval method.

The secondary evaluation indicators are evaluated by the difference test. Measurement data are compared using two independent samples t-test. Enumeration data are compared using Pearson's  $X^2$  test or Fisher's

exact test.

The safety evaluation indicators are evaluated by the difference test. Measurement data are compared using two independent samples t-test. Enumeration data are compared using Pearson's  $X^2$  test or Fisher's exact test. The adverse events and device defects occur in this trial shall be shown in list.

The stapler operational performance is evaluated by the difference test, with the Pearson's  $X^2$  test or Fisher's exact test.

The central effect is considered in the analysis process. The general linear model is used for measurement data, and CMH is used for enumeration data.

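### Postoperative laboratory and vital-sign values are to be analysed without the subject's own Visit 1 value, which gives up precision that the collected data would allow (minor)

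*Combined protocol and SAP*

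**What the plan says.** All references are to the combined protocol and SAP.

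- **What must be analysed.** Section 8.1.8(6), under the incidence of adverse events, states: "It is necessary to analyze the postoperative vital signs and laboratory tests (blood routine, biochemical indicators, etc".
- **What is measured before surgery.** Section 8.2.7.1 (Visit 1, Day -7 to 0) lists vital signs and "Performing laboratory examinations (blood routine, coagulation routine, blood biochemistry, heart examination, pulmonary function test, arterial blood gas analysis, blood pregnancy test".
- **What is measured after surgery.** Section 8.2.7.3 (Visit 3, Day 7 ± 2) lists vital signs and "Conducting laboratory examinations (blood routine, coagulation routine, blood biochemistry". Vital signs are also taken at Visits 2 and 4.
- **How continuous data are compared.** Section 9.7.1 gives the same sentence for secondary and for safety indicators: "Measurement data are compared using two independent samples t-test".
- **The other model.** The same section adds "The central effect is considered in the analysis process" and "The general linear model is used for measurement data, and CMH is used for enumeration data". It does not say how that model relates to the t-test, and it names no covariate other than centre.
- **Where the detail is to go.** Section 9.1 defers full methods to a statistical analysis plan finalised before database lock. Section 9.8 treats analyses that were not pre-specified there as exploratory only.

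**The concern.** The seven safety indicators in section 8.1.8 are all incidences: dehiscence, bleeding, air leakage, infection, SAEs, AEs and device defects. The laboratory and vital-sign values of 8.1.8(6) are therefore the only continuous safety data to which the t-test sentence under safety in 9.7.1 can apply. Every such value has a preoperative counterpart from the same subject, yet neither the t-test nor the centre model uses it.

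Part of the spread in a postoperative haemoglobin, creatinine or blood pressure is spread that the subject brought to the operation. A two-sample t-test on postoperative values leaves that part in the error term, whereas a model with the Visit 1 value removes it. What is at stake is the sharpness of the comparison between devices on these supporting safety data. The trial was sized for the binary primary endpoint alone, so any gain in precision on these values has to come from the analysis.

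**Working it through.** **1. The plan's own sample size (section 9.2.1).** Inputs: success rate 97% in both arms, margin 10 percentage points, one-sided α 0.025, power 80%, ratio 1:1, dropout 20%.

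- n₃ = 2 × 0.97 × 0.03 × (0.8416 + 1.9600)² / 0.10² = 45.68
- n₄ = 45.68 × {1 + √[1 + 4/(0.10 × 45.68)]}² / 4 = 64.12, rounded up to 65 per arm
- 65 / (1 − 0.20) = 81.25, rounded up to 82 per arm, 164 in total

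The stated figures reproduce. They do not depend on how laboratory values or vital signs are analysed. The plan gives no power or precision figure for those data.

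**2. Effect of adding the Visit 1 value.** Let r be the within-arm correlation between the Visit 1 and Visit 3 values. The documents give none, so r = 0.3, 0.5 and 0.7 are assumptions. With baseline in a linear model:

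- residual variance = (1 − r²) × SD²
- interval width is multiplied by √(1 − r²)
- equivalent size per arm for an unadjusted test = n / (1 − r²)
- a shift of d SD becomes d / √(1 − r²) residual SDs

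Power is from the noncentral t distribution with 2n − 2 degrees of freedom and noncentrality d√(n/2)/√(1 − r²). The test is taken as two-sided at 0.05: section 9.5 gives 0.05 for the difference tests without stating sidedness. The shift of 0.4 SD is an illustrative assumption. The few degrees of freedom used by centre and baseline are ignored.

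| | t-test on postoperative values | r = 0.3 | r = 0.5 | r = 0.7 |
|---|---|---|---|---|
| 1 − r² | 1 | 0.91 | 0.75 | 0.51 |
| Interval width, multiplied by | 1 | 0.95 | 0.87 | 0.71 |
| Equivalent per arm, n = 82 | 82 | 90 | 109 | 161 |
| Power for 0.4 SD, n = 82 | 72% | 76% | 84% | 95% |
| Power for 0.4 SD, n = 65 | 62% | 66% | 74% | 89% |

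Example at n = 82 and r = 0.5: 0.4/√0.75 = 0.462 residual SDs; noncentrality 0.462 × √41 = 2.96; power 84%.

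**3. If the t-test were meant for changes from baseline.** Section 9.7.1 does not say whether raw values or changes are compared. With equal SDs at the two visits, a change score has variance 2(1 − r) × SD², that is 1.4, 1.0 and 0.6 times SD² for the three correlations. The adjusted model gives 0.91, 0.75 and 0.51. Adjustment is more precise on either reading, and at r = 0.3 a change score is noisier than the raw postoperative value.

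**The case against.** The strongest reply is that this is a preference about efficiency, not an error. An unadjusted t-test in a randomised trial is unbiased. Laboratory and vital-sign values are not among the seven listed safety indicators; they appear in one sentence under the AE definition, with no hypothesis or success criterion attached. Full methods are deferred to a separate statistical analysis plan, so silence here does not prove that no baseline term is intended. The size rests on assumed correlations, and at r = 0.3 the gain is about 5% in width and 4 points of power. The t-test on postoperative values also keeps subjects whose Visit 1 value is missing, and section 9.7.2 does not impute baseline data.

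All of that stands, and it sets the priority. It does not remove the point. Section 9.7.1 is the only method text supplied, and it names no baseline term. Section 9.8 means that a model chosen after the plan is final would count as exploratory.

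A reader might infer more, in three ways that the documents do not support:

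- **Operation time has the same defect.** It does not. It is a single intraoperative duration (section 8.1.7.2(1)), so no baseline value exists. Adjusting it for adhesion extent or planned procedure is a different argument with no gain quantified, and exclusion criterion (2) is aimed at severe pleural adhesions.
- **The resection-site list is part of this problem.** Footnote 9 in section 8.2.5.5 gives "Right upper lobe, right middle lobe, right lower lobe, left upper lobe and left lower lobe" and no segments. That is a separate question of coding.
- **Lost precision lets the sponsor claim equivalence.** Section 9.5 reads p > 0.05 only as no significant difference in that indicator. The sole non-inferiority criterion there concerns the primary success rate.

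**Conclusion.** The point holds for postoperative laboratory and vital-sign values only, and it is minor. The plan collects each subject's preoperative value, requires the postoperative values to be analysed, and names no analysis that uses the two together. The cost is precision, not validity: intervals for the device difference would be about 5% to 29% narrower with adjustment, for assumed correlations of 0.3 to 0.7. Power for a 0.4 SD shift would be about 4 to 23 points higher at 82 per arm (72% against 76% to 95%) and about 4 to 27 points higher at 65 per arm (62% against 66% to 89%).

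These figures rest on the assumed correlations and shift, on a two-sided 0.05 test, and on the t-test being applied to raw postoperative values, which the text does not state. The non-inferiority conclusion, its type I error and the sample size are untouched.

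**What to change.** In section 9.7.1 and in the statistical analysis plan, before database lock, state that postoperative laboratory and vital-sign values are analysed by the general linear model already named, with arm, centre and the subject's own Visit 1 value as terms. Report the adjusted difference between arms with its 95% interval. Say that this model replaces the t-test for these data, so that there is one stated analysis and the question of raw values or changes does not arise.

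The cost is a few lines of wording. No new data, visits or subjects are needed. The one drawback is that a subject with a missing Visit 1 value drops out of the model for that variable, because baseline data are not imputed; the number lost should be reported for each variable.

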#### 8.2.3 Randomization

The trial was stratified by clinical trial institutes with the randomization method of stratified blocks. The seed number and block length were determined with SAS9.1 statistical software programming. The subjects were divided into the test group and the control group in a ratio of 1:1. The random grouping arrangement of at least 164 subjects was generated, and the corresponding sequentially numbered, opaque and sealed randomization envelopes were made. The randomization envelopes were kept and allocated by relevant personnel who were not involved in the screening and treatment of subjects and authorized by the investigator.

The random number is a 4-digit sequential number consisting of "center number" and "serial number". The first digit is the number of the clinical trial institution, and the last 3 digits are the "serial number" assigned by randomization. When the serial number is less than 3 digits, add "0" to make up 3 digits. If the randomization number "1001" is the first randomization number of the clinical trial institute with the institute number of 01, it corresponds to the first subject randomized at the institute.

When a subject was determined to be enrolled, the investigators or other authorized designee requested randomization assignment from the randomization envelope manager. The randomization envelope keeper took out the randomization envelope in the order of random number, filled in the screening number and initials of the subject to be assigned to the designated place on the back of the envelope, and signed the name and date to complete the allocation. The investigators or other authorized designee then intervened based on the results of the randomization assignment (i.e., test groups).

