### 9.5 Qualification/Disqualification Criteria for Clinical Trial Results

The non-inferiority hypothesis is tenable if the lower limit of 95% confidence interval of the difference in the primary effectiveness evaluation indicator "device cutting and anastomosis success rate" between the test group and the control group is greater than the non-inferiority critical value (-10%).

The secondary effectiveness evaluation indicators and safety evaluation indicators are tested by difference test, and the significance level is set at 0.05. If the test result of the difference in any secondary evaluation indicator and safety evaluation indicator between the test group and the control group is p > 0.05, then there is no significant difference in this indicator between the test group and the control group.

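### For the secondary and safety indicators the plan names both unadjusted and centre-adjusted tests without saying which p-value enters the 9.5 rule; for measurement data the unadjusted t-test is conservative if centres differ

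*Combined protocol and SAP*

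**What the plan says.** Section 8.2.3: "The trial was stratified by clinical trial institutes with the randomization method of stratified blocks". Section 8.1.3 also gives the study site as the stratification factor.

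Section 9.5: "The secondary effectiveness evaluation indicators and safety evaluation indicators are tested by difference test", at a significance level of 0.05. If p exceeds 0.05, "then there is no significant difference in this indicator between the test group and the control group".

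Section 9.7.1 sets out two layers of analysis:

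- The first layer is the difference test: "The secondary evaluation indicators are evaluated by the difference test" and "The safety evaluation indicators are evaluated by the difference test". For both groups of indicators, "Measurement data are compared using two independent samples t-test", and enumeration data go to Pearson's chi-square or Fisher's exact test. None of these has a centre term.
- The second layer is one closing paragraph: "The central effect is considered in the analysis process" (meaning the effect of centre), with a general linear model for measurement data and CMH for enumeration data.

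The statistical part of the protocol abstract has the same two layers. Neither place says whether the second layer replaces, supplements or checks the first. Section 9.1 leaves the details to a statistical analysis plan to be finalised before database lock.

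**The concern.** Blocking 1:1 within centre balances the arms in every centre. Differences between centres then cancel, nearly completely, from the treatment comparison. They stay in the standard error of an unadjusted t-test, which is therefore too large on average, so the test rejects too rarely.

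The direction matters because 9.5 reads p > 0.05 as no significant difference. A test with less power than the design offers makes that reading easier to reach, including for a real disadvantage of the test device.

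The protocol itself gives reasons to expect centre differences. It refers to different regions and many researchers (8.1.3), a learning curve and dependence on operating skill (8.1.4), and different case sources by centre (9.2.3). Operation time and anastomosis time are the indicators most likely to show them.

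**Working it through.** **Inputs from the documents.** 5 centres with 16 to 60 subjects each (9.2.3); 1:1 allocation, 82 per group, 164 in total (9.2.1); level 0.05 (9.5; sidedness is not stated, read here as two-sided).

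**Assumed inputs.** The share ρ of outcome variance lying between centres, blocks of 4, and the event rates below. The documents give none of these.

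**The plan's own figure.** The only sample size calculation is for the primary endpoint, and it reproduces:

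- n₃ = 2 × 0.97 × 0.03 × (0.8416 + 1.96)² / 0.10² = 45.68
- n₄ = 45.68 × [1 + √(1 + 4/(0.10 × 45.68))]² / 4 = 64.12, so 65
- 65 / 0.8 = 81.25, so 82 per group and 164 in total

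No figure is given for the secondary or safety tests.

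**Measurement data, formula.** Let σ² be the total variance. With arms balanced within centre, the mean difference has variance 2σ²(1 − ρ)/82, but the unadjusted t-test estimates it as 2σ²/82. Hence unadjusted z = adjusted z × √(1 − ρ), and the unadjusted test rejects only when the adjusted |z| exceeds c = 1.96/√(1 − ρ).

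- True error = 2 × [1 − Φ(c)].
- Power, at a difference for which the adjusted model has 80%, = Φ(2.8016 − c). With 82 per group that difference is 2.8016 × √(2/82) = 0.44 within-centre SD.

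| ρ (assumed) | c | True error, unadjusted | Power, unadjusted | Power, adjusted |
|---|---|---|---|---|
| 0 | 1.960 | 5.0% | 80% | 80% |
| 0.10 | 2.066 | 3.9% | 77% | 80% |
| 0.20 | 2.191 | 2.8% | 73% | 80% |
| 0.30 | 2.343 | 1.9% | 68% | 80% |

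For a given ρ the true error does not depend on the number analysed. On the same formula, an unadjusted p of 0.08 (z = 1.751) corresponds to an adjusted p of about 0.065, 0.050 or 0.036 at ρ = 0.10, 0.20 or 0.30.

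**Check by simulation.** 164 subjects, 5 centres, blocks of 4, 3000 trials per cell. Here the difference is fixed at 0.44 *total* SD, so adjusted power rises with ρ instead of staying at 80%.

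| Centre sizes | ρ | Error, t-test / model | Power, t-test / model |
|---|---|---|---|
| 33, 33, 33, 33, 32 | 0 | 0.048 / 0.047 | 0.802 / 0.803 |
| 33, 33, 33, 33, 32 | 0.10 | 0.045 / 0.057 | 0.797 / 0.828 |
| 33, 33, 33, 33, 32 | 0.20 | 0.030 / 0.050 | 0.823 / 0.878 |
| 33, 33, 33, 33, 32 | 0.30 | 0.018 / 0.051 | 0.827 / 0.918 |
| 60, 40, 28, 20, 16 | 0.10 | 0.038 / 0.050 | 0.815 / 0.838 |
| 60, 40, 28, 20, 16 | 0.20 | 0.029 / 0.047 | 0.823 / 0.884 |
| 60, 40, 28, 20, 16 | 0.30 | 0.024 / 0.055 | 0.833 / 0.914 |

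The pattern agrees with the formula for equal and unequal centres. With no centre variation, adjustment costs nothing measurable.

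**Binary data.** Simulation with the near-equal centre sizes, 2500 trials per cell, all event rates assumed; power is at an odds ratio of 3.

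| Average control rate (range over centres) | Error, Pearson / Fisher / CMH | Power, Pearson / Fisher / CMH |
|---|---|---|
| about 3% (0–8%) | 0.044 / 0.013 / 0.045 | 0.28 / 0.19 / 0.30 |
| about 10% (2–25%) | 0.046 / 0.032 / 0.056 | 0.64 / 0.58 / 0.67 |
| about 30% (5–65%) | 0.028 / 0.018 / 0.048 | 0.78 / 0.73 / 0.85 |

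For rare events Pearson and CMH barely differ, and the conservatism of Fisher's test is far larger than the effect of centre.

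**The case against.** A reader might infer that the centre-adjusted models decide nothing. The documents do not support that. Section 9.5 names no procedure beyond a difference test; the linear model and CMH also test a difference; and the closing paragraph of 9.7.1 says that they are used, so it can be read as the operative rule. What can be shown is that two analyses exist for each indicator and that neither is named as governing.

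A reader might also infer that all secondary and safety p-values are too large. Of the twelve indicators only three are measurement data. The other nine are rates, for which the effect runs from negligible to modest unless centres differ widely. Even for measurement data it is a tendency on average, not a property of each p-value.

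Nor do the documents leave a free choice once results are known. Section 9.1 requires an analysis plan before database lock, and 9.8 in general confines the report to pre-specified analyses. This narrows the worry but does not settle it: both analyses are named in the protocol, so either would count as pre-specified unless the plan ranks them.

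Finally, an unadjusted test under stratified randomisation does not inflate false positives, and 9.5 attaches no non-inferiority margin to these indicators. Both points are correct and keep the matter small.

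**Conclusion.** The point holds as a modest, easily corrected weakness. The wording of 9.5 and 9.7.1 ties the secondary and safety rule most directly to tests that ignore the randomisation stratum, and gives the planned centre-adjusted analyses no stated place in that rule.

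The loss for measurement data is small at a 10% between-centre share (3 points of power) and material at 30% (12 points). Those shares are assumptions, and the figures are for roughly normal outcomes. They fit the two times better than the number of repair needles, which is a count. For rare events such as dehiscence, infection or conversion (rarity also assumed), the choice of analysis makes almost no difference. The primary non-inferiority rule and the sample size of 164 are unaffected.

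**What to change.** In 9.5, 9.7.1 and the statistical analysis plan, name one governing analysis per indicator and tie the 0.05 rule to its p-value:

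- **Measurement data** (operation time, anastomosis time, number of repair needles): general linear model with treatment and centre, reporting the adjusted difference and its 95% confidence interval.
- **Per-subject rates:** CMH stratified by centre, with an exact version when events are sparse. State that strata without events contribute nothing; at an assumed 3% there would be about five events in all (0.03 × 164 = 4.9), so empty strata are likely.
- **Unadjusted t-test, Pearson and Fisher results:** reported as supportive.

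Device-defect incidence is counted per device (8.1.8), so a per-subject CMH does not carry over, and it stays outside this change.

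The cost is a few sentences. Both analyses are already planned, apart from the exact version, and no extra subjects or data are needed. The wording should be settled before database lock.
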